#### Sample II: Spit for Science - The VCU Student Survey

The proposed research will attempt to replicate the findings from the [discovery] sample in a new sample of undergraduate students enrolled in VCU's Spit for Science (S4S) project (Phase I). Replicating the polygenic factors obtained in a discovery dataset, in an independent sample, is a critical step in building cumulative scientific knowledge. Among a subset of participants in the Spit for Science sample, brain imaging will be used to identify the neural mechanisms of polygenic risk for alcohol-influenced aggression (Phase II).

#### Phase I - Replication in S4S Sample

Participants. At the outset of each academic year, incoming first-year VCU undergraduates are invited to participate in the S4S project via an online survey, and they have the option to provide a saliva sample that will be genotyped. Compensation is \$10. From 2011-2014, S4S has enrolled six consecutive cohorts (68% average enrollment from incoming freshman, average cohort  $N = \sim 2,500$ ). Of those individuals who completed the initial online component, 97% provided a saliva sample for genotyping. Participants in the sample reflect general demographics among VCU students, which are relatively diverse (40% male, 60% female; 51% White, 19% African American, 15% Asian, 6% Hispanic/Latino, and 9% other/multiracial/unknown). Increasing freshman class sizes have magnified the S4S cohort sizes in recent years to approximately 3,300 participants per cohort.

Genotyping and imputation. Genotyping is performed at Rutgers University Cell and DNA Repository (RUCDR) using the Affymetrix BioBank array. The 653,000 gene variants included in this array contain 296,000 common GWAS framework variants for imputation as well as 357,000 functional variants. Quality control uses AffyPipe analysis pipeline to exclude Off Target Variants, SNPs missing > 5% of genotypes, samples missing > 2% of genotypes, and SNPs missing > 2% of genotypes after sample filtering. Samples will be imputed to 1000 Genomes using SHAPEIT and then IMPUTE2.

Phenotype measures. The same SSAGA questions from the [discovery samples] about alcohol-influenced aggression will be added to the existing online survey administered to all new S4S participants at the onset of their participation. The S4S online survey already includes demographic assessments. These surveys will be administered in the fall of 2018, 2019, and 2020.

#### Analytic Plan

[S4S data will undergo the same GWAS and risk score procedures as employed in the discovery dataset.]

#### Feasibility

This first phase of Aim II builds upon the already successful and ongoing S4S project, by simply adding a short online survey to the existing S4S battery of questionnaires. However, undergraduates at VCU differ from the [diverse members of the discovery sample] in ways that may suppress the amount of alcohol-influenced aggression among the S4S sample (e.g., lower levels of alcohol misuse and dependence). A pilot sample of VCU undergraduates were asked about their aggressive behavior and whether it occurred in the context of

alcohol misuse or not. Of the 166 female and male participants surveyed, 53.6% indicated that they had participated in a physical fight in the past 5 years (30.1% had been in more than 1 fight). Of those who had previously fought, 38.2% participated in this fight under the influence of alcohol. These initial estimates suggest that 1 out of 5 VCU undergraduates (i.e., 20.48%) have perpetrated a substantial act of physical aggression under the context of alcohol misuse. This prevalence rate indicates that the much larger pool of potential S4S participants is likely to exhibit alcohol-influenced aggression at a sufficient rate to test associations with polygenic risk scores.

Power analysis. The expected S4S sample size of 10,000 students will provide 80% power to detect a genome-wide effect of 0.35% variance explained in alcohol-influenced aggression, or larger. [The S4S GWAS is likely to be under-powered, yet performing this replication GWAS will serve as a valuable training in how to collect genomic data and use it to replicate previous GWAS results.]

Potential Problems and Alternative Strategies. The S4S sample GWAS may not replicate the profile of SNPs found in the [discovery] sample, as the S4S sample is smaller and is comprised of undergraduate students. However, replication is a crucial step in genomic science and this is as important training experience.

#### Phase II - Investigating Neural Mechanisms in an S4S Sub-Sample

[figure not shown]
Participants. From the 2018-2020 cohorts of the S4S sample, I will recruit [202] individuals with low ( $N = 101$ ) and high ( $N = 101$ ) polygenic risk scores for alcohol-influenced aggression for a brain imaging experiment. Participants [will be equal numbers of males and females and] are expected to reflect the ethnic/racial makeup of the larger S4S sample which is relatively diverse (40% male, 60% female; 51% White, 19% African American, 15% Asian, 6% Hispanic/Latino, and 9% other/multiracial/unknown). Ages will range from 21-35 to ensure that only adults complete the study, that they can legally consume alcohol, and that aging effects do not influence our MRI data.

Recruitment and Screening. I will recruit VCU students who enrolled in the 2018-2020 cohorts of the S4S study, using their existing contact information in the S4S participant database. Participants will be recruited based on their polygenic risk scores that were obtained from the [discovery] GWAS. The S4S GWAS will not be used to establish the polygenic risk scores used to recruit these participants as they draw from the same pool of individuals. Establishing polygenic effects on behavior requires replication in an independent sample, as the use of dependent samples artificially inflates association statistics. Recruitment based on polygenic risk scores will proceed by contacting individuals from the lowest end of the distribution of polygenic risk scores (low risk group) and the highest end of the distribution of risk scores (high risk group), working from both ends of the distribution towards the median. Individuals who are contacted based on their risk scores will be screened with an online survey various conditions that would make the alcohol administration and MRI scanning procedures unsafe or invalid (see Protection of Human Subjects for a detailed list) and will be contacted to schedule an appointment if they pass these criteria.

MRI [Sessions]. [The MRI study will take the form of a two-session experiment, in which alcohol or placebo beverages are administered to each participant in a counterbalanced order. In Session 1,] participants will arrive at VCU's Collaborative Advanced Research Imaging (CARI) facility where they will repeat the screening procedures and then will practice the computer tasks that they will perform in the scanner. Then, participants will be told that they will receive [either] a placebo [or] an alcoholic beverage, but that they will not be informed of the nature of each beverage until the end of the study (see Figure 4 for the MRI scan timeline). [By random assignment,] participants will then consume [either a placebo beverage of orange juice with 4ml ethyl alcohol added to the rim or an alcoholic beverage

consisting of a 1:5 ratio of 95% ethyl alcohol and orange juice. The alcohol dose will be proportional to participants' body weight and sex, due to sex differences in body fat composition and alcohol metabolism (females: 0.9 g/kg ethyl alcohol; males: 1.0 g/kg ethyl alcohol). This alcohol dose typically increases participants' breath-alcohol-concentration to .08%, the legal driving limit in Virginia.] After consuming the beverage, participants will then be placed in the MRI scanner and complete a validated laboratory aggression paradigm that allows individuals to "hurt" a fictitious opponent with an aversive noise blast, while undergoing echo-planar functional MRI (EPI). In this task, participants compete against an opponent to press a button faster, and the loser of the competition then hears an aversive noise blast. Aggression is operationalized as the

Figure 4. Timeline of both MRI sessions.

volume of the noise blast (65-105 decibels) that participants select for a fictional opponent who repeatedly provokes them by selecting extremely loud noise blasts. After completing these scans, [participants will leave and return to the CARI center 7 days later for Session 2. Participants will consume either a placebo (if they consumed an alcoholic beverage in Session 1) or an alcoholic beverage (if they consumed an alcoholic beverage in Session 1), and then will be returned to the scanner to complete the aggression paradigm a second time against a new provocative opponent.] Participants will be told that both of their opponents are same-sex VCU undergraduates, when in fact, they are computer programs.

After completing the aggression task, participants will undergo diffusion tensor imaging (DTI), which quantifies the integrity of white matter pathways, and a high-resolution T1 scan, which quantifies gray matter density (see Figure 5 for a depiction of each brain imaging modality). Participants will be removed from the

[figure not shown]
MRI scanner and allowed to relax in a nearby testing room until their BAC is between .02-.04%. [At the end of Session 2, an experimenter will briefly interview each participant to assess their suspicion of our deception during the study, debriefed as to the true purposes of the study, provided with counseling resources in case of distress, and then paid \$100 for their participation. Participants who guess that they had no actual partners or that the goal of the study was actually to measure aggression will be excluded from all data analyses]

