#### Potential Problems and Alternative Strategies

Participants in the low and high polygenic risk groups will likely differ on other variables (e.g., physical health) that might serve as problematic confounds. To address this, participants from each group will be closely-matched on age, sex, race, and socioeconomic status. The groups will be equated in physical and mental health as the screening procedures exclude any individuals with diagnosed physical or mental pathologies. There are also risks posed by the MRI environment, alcohol administration, and aggression task procedures. I have extensive MRI experience, participants undergo extensive screening procedures, and participants are under constant supervision by CARI center staff who are certified in safe MRI and alcohol administration procedures. CARI center staff are prepared to effectively handle any potential medical emergencies. If a brain abnormality is observed, a licensed radiologist is available through the CARI facility for consultation. The success of this study hinges on effective participant recruitment. Multiple offshoot studies using S4S data have been successful (e.g., an F31-funded fMRI study in [name] lab that recruits S4S participants for based on polygenic risk scores for externalizing behaviors). Further, the recruitment pool is large enough to provide many potential participants who meet this study's inclusionary criteria.

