**Table 3. Research activities by award year (Y).**

Activity	Y1	Y2	Y3	Y4	Y5
[Discovery] data preparation	X				
[Discovery] data analysis	X	X			
[Discovery manuscript submission]			[X]		
S4S genotyping data collection	X	X			
S4S genotyping data analysis			X		
[S4S genotyping manuscript submission]			[X]		
S4S neuroimaging data collection			[X]	X	
S4S neuroimaging data analysis					X
[S4S neuroimaging manuscript submission]					[X]
R01 application preparation				X	X
[R01 application submission]					[X]

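### Imaging draws only on the 2018-2020 first-year cohorts but needs people aged 21 or over in award years 3-4; the plan never counts who qualifies, and on the likely calendar the risk-score contrast falls by about 6-21%

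*Combined protocol and SAP*

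**What the plan says.** Four statements bear on the point.

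- **Source.** Phase II, Participants: "From the 2018-2020 cohorts of the S4S sample, I will recruit [202] individuals", split 101 low and 101 high risk. Recruitment and Screening repeats the limit: "I will recruit VCU students who enrolled in the 2018-2020 cohorts of the S4S study". No other S4S cohort is named.
- **Age.** Same section: "Ages will range from 21-35 to ensure that only adults complete the study". Legal drinking age and the avoidance of ageing effects on the scans are also given as reasons.
- **Entry.** Phase I says that "incoming first-year VCU undergraduates are invited to participate in the S4S project via an online survey". Of the new survey items it says: "These surveys will be administered in the fall of 2018, 2019, and 2020". Recent intakes are "approximately 3,300 participants per cohort".
- **Timing.** Table 3 marks the row "S4S neuroimaging data collection" in Y3 and Y4.

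Recruitment starts at the two extremes of the polygenic score and moves inward until the groups are full. The score comes from the discovery GWAS only. On feasibility, Potential Problems and Alternative Strategies says that "the recruitment pool is large enough to provide many potential participants". No count by age supports this.

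**The concern.** A student who enters at 18 or 19 reaches 21 two to three years later. The frame, the age limit and the scanning window therefore pull against one another, and much of the nominal pool may not be eligible when scanning takes place.

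What is at stake is the contrast between the groups more than the head count. Under extreme-group selection, the mean score difference depends on how far into each tail recruitment can stay. With fewer eligible students, the same 101 per group must come from nearer the median. The groups then differ less in genetic risk, and any effect that scales with the score becomes harder to detect. Equal numbers of each sex, the health exclusions, and matching on age, sex, race and socioeconomic status narrow the pool further.

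**Working it through.** **The plan's own figures.** Three cohorts of 3,300 give 3 × 3,300 = 9,900, which agrees with the 10,000 stated in the Phase I power analysis. With 97% providing saliva, 9,900 × 0.97 = 9,603. The imaging target also reproduces: 198 + 4 = 202.

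**Assumptions.** The documents do not give the calendar date of Y1, the age at entry, or the uptake among those contacted. I take entry in September at an age uniform on 18.0-19.0, and vary the Y1 date and the uptake. September 2018 is the base case because the new survey items start in fall 2018 and S4S data collection begins in Y1.

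**Eligible share.** For a cohort entering in September of year c, the share aged 21 or over at time t is (t − c) − 2, held between 0 and 1. In the base case:

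| Time | 2018 cohort | 2019 cohort | 2020 cohort | Whole pool |
|---|---|---|---|---|
| Start of Y3 (Sept 2020) | 0 | 0 | 0 | 0% |
| End of Y3 (Sept 2021) | 1 | 0 | 0 | 33% |
| Mid-Y4 (March 2022) | 1 | 0.5 | 0 | 50% |
| End of Y4 (Sept 2022) | 1 | 1 | 0 | 67% |

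The average over the window is 33%. At the end of Y3 about 3,200 of the 9,603 qualify, and at the end of Y4 about 6,400. The 2020 cohort reaches 21 only after Y4, apart from older entrants. If 10% of entrants are already over 21, the average is 40%; if entry age is 18.25-19.25, it is 42%.

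By date of Y1:

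| Y1 starts | Average over Y3-Y4 | End of Y4 |
|---|---|---|
| September 2017 | 8% | 33% |
| July 2018 | 28% | 61% |
| September 2018 | 33% | 67% |
| January 2019 | 44% | 78% |
| July 2019 | 61% | 94% |

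Recruitment cannot simply wait for late Y4. At the 112 participants per year quoted in the Phase II feasibility text, 202 / 112 = 1.8 years are needed.

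**Contrast for a fixed pool.** With tail share f = 101 / (pool × uptake) and a normal score, the high-low difference is 2·φ(z)/f SD, where z is the upper-f normal quantile. At 10% uptake:

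- three cohorts: f = 101/960.3 = 0.105, contrast 3.46 SD;
- two cohorts: f = 101/640.2 = 0.158, contrast 3.06 SD;
- one cohort: f = 101/320.1 = 0.316, contrast 2.25 SD.

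**Contrast with accrual over the window.** The pool grows during Y3-Y4, so I simulated even monthly accrual over 24 months, each month taking the most extreme students who had reached 21.

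| Uptake | No age limit | Y1 Sept 2018 | Loss | Loss, July 2019 | Loss, Sept 2017 |
|---|---|---|---|---|---|
| 100% | 5.29 SD | 4.97 SD | 6% | 1% | 38% |
| 50% | 4.79 | 4.43 | 8% | 1% | 36% |
| 20% | 4.09 | 3.68 | 10% | 1% | 41% |
| 10% | 3.47 | 3.02 | 13% | 3% | 44% |
| 5% | 2.75 | 2.16 | 21% | 4% | 42% |

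All 202 were recruited in every cell except September 2017 at 5% uptake, where 154 were. If 10% of entrants are over 21, the base-case loss is 5-17%. Matching and the equal-sex rule are not modelled.

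**Effect on power, as illustration only.** The 80% stated for 198 participants cannot be rebuilt from the plan's inputs. A standardised difference of 0.4 happens to need 99 per group. If that were the target and the effect scaled with the contrast, a 10% loss would give 72% power and a 20% loss 61.5%.

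**Adding earlier cohorts.** Phase I speaks of six cohorts for 2011-2014, a span of four years, so I use four: 4 × 2,500 × 0.97 = 9,700. With one new cohort of 3,201 and 10% uptake, f = 101/1,290.1 = 0.078 and the contrast is 3.74 SD. That exceeds the 3.46 SD from all three new cohorts together. If uptake among earlier entrants is only 2%, the recruitable pool is 194 + 320.1 = 514.1, f = 0.196 and the contrast is 2.82 SD. That is still above the 2.25 SD from one new cohort alone.

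**The case against.** A reader might infer that most of the pool is simply too young. The documents do not support that without conditions. In the base case it holds on average and until about mid-Y4, but two thirds qualify by the end of Y4. With Y1 in July 2019 it fails for most of the window.

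The base calendar is itself uncertain. Table 3 confines S4S genotyping collection to Y1-Y2, yet with Y1 from September 2018 the fall 2020 intake falls in Y3. All three fall surveys fit into 24 months only if Y1 starts partway through fall 2018. Either the start is later than assumed or Table 3 is approximate. This stands, and is why the result is given as a range.

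A reader might also infer that 202 cannot be reached. In the base case it can, even at 5% uptake. One cohort of about 3,200 genotyped students is roughly 16 times the target, and the plan states no required score contrast. The adequacy claim is therefore unsupported rather than refuted.

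Finally, widening the frame has limits. Phase I reports that earlier participants gave saliva for genotyping; it does not say that their genotyping is complete. Former students may respond less. The opponents are presented as current undergraduates, which older participants may find less credible, and those who see through the deception are excluded. The available text of the Phase II analysis is broken, so a use for the new survey items there cannot be ruled out, although no described procedure needs them. These points qualify the fix but do not remove the conflict.

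**Conclusion.** The concern holds in conditional form. The cohort restriction, the age range and the Y3-Y4 window conflict in timing, and the plan neither notices this nor counts the eligible pool. The direction is certain: fewer eligible students means selection nearer the median. The size rests on three unstated quantities: the date of Y1, age at entry and uptake. With Y1 from about fall 2018 and entry at 18-19, the contrast loss is modest at high uptake and reaches about a fifth at 5%, before matching. It is close to nothing if the award starts in mid-2019 and severe if it started in fall 2017. The harm in the base case is a weaker contrast rather than a failure to recruit. This should be corrected before recruitment begins.

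**What to change.** 1. In Phase II, Participants and Recruitment and Screening, replace the restriction to the 2018-2020 cohorts with all S4S participants who have usable genotypes and are within the plan's stated age range at scanning. Score them with the discovery weights. Leave the age range as it is.
2. Give calendar dates for the award years in Table 3, and reconcile them with the fall survey dates and the genotyping window.
3. Tabulate eligible genotyped participants by cohort and quarter of the scanning window, after screening and matching, with the uptake assumed. State the score contrast expected, and rest the pool-adequacy claim on that count.
4. Correct the number of earlier cohorts in Phase I.

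The cost is mainly wording, one table and access to existing contact records. The plan should name the downsides: lower reach and uptake among earlier participants, the need to confirm that their genotyping is complete, a wider age spread for the matching to handle, and a cover story that may convince older participants less.

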**Genome-wide association study (GWAS).** After the GCTA, GWAS will be used to identify single nucleotide polymorphisms (SNPs) and clusters of SNPs that are significantly associated with alcohol-influenced aggression. Due to the skewness of the alcohol-influenced aggression scores (see Figure 3), quasi-Poisson regression analyses will be used to accommodate such a distribution using the Bioconductor v2.1 package and SNPTEST v2.5. Specifically, alcohol-influenced aggression scores will be regressed onto principal components of the available SNPs using an additive model, excluding non-autosomal SNPs, with demographics factors as covariates. Due to racial stratification, separate GWAS will be performed for participants of African, American, East Asian, European, South Asian, and Mixed Race descent. Participants will be empirically assigned to these ancestral super-populations using the 1KGP population base and the Mahalanobis' distance between each population. I will meta-analyze these separate sets of GWAS findings METAL v3.0^32, which will produce meta-analytic '% variance explained' effect size estimates and  $p$  values for each SNP. [In addition to this meta-analytic approach, I will test for gene-by-race/ethnicity moderation using a kernel-machine approach to estimate whether each SNP's association with alcohol-influenced aggression varies across the discovery sample's diverse racial/ethnic groups, using the Robust Joint Tests package.] After correction for genetic inflation and weighting based on sample size, I will calculate polygenic risk scores for alcohol-influenced aggression [based on SNPs meeting increasingly stringent significance thresholds: .5, .4, .3, .2, .1, .05, .01, .001, .0001. The threshold that maximizes the variance explained ( $R^2$ ) in alcohol-related aggression will be used for risk score calculation.] Using an additive approach, I will sum across the number of alleles that are significantly linked to the phenotype, weighted by their respective effect size estimates from the GWAS. For example, if the A allele (versus the corresponding G allele) of a given SNP is significantly associated with greater alcohol-influenced aggression, then each copy of the A allele will be initially coded as +1 (GG = 0, GA = 1, AA = 2). These scores will then be multiplied by the GWAS effect size estimate for that given SNP. This polygenic risk scores will capture aggregate genetic risk for alcohol-influenced aggression in a manner that represents the current state of the field.

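### Imaging recruitment from the score extremes has no stated ancestry step or link to the promised race matching; if mean scores differ by ancestry, the literal order confounds risk group with ancestry.

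*Combined protocol and SAP*

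**What the plan says.** **Recruitment order.** Under Phase II, Recruitment and Screening, low-risk participants are contacted from the bottom of the score distribution and high-risk participants from the top, "working from both ends of the distribution towards the median". One distribution is described. No ancestry stratum is named.

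**Score.** In the discovery Analytic Plan (GWAS paragraph), "separate GWAS will be performed for participants of African, American, East Asian, European, South Asian, and Mixed Race descent". The results are then combined: "I will meta-analyze these separate sets of GWAS findings METAL v3.0". The score is the sum of allele counts weighted by the resulting effect sizes. No centring, scaling or residualising by ancestry is stated. The fallback score, a product of two external scores (discovery-sample Potential Problems and Alternative Strategies), has no ancestry step either.

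**Composition.** The Phase II Participants paragraph says that those recruited "are expected to reflect the ethnic/racial makeup of the larger S4S sample", given as "51% White, 19% African American, 15% Asian, 6% Hispanic/Latino, and 9% other/multiracial/unknown". It also calls for equal numbers of men and women.

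**Matching.** The Phase II Potential Problems and Alternative Strategies section expects the risk groups to differ on other variables and answers that "participants from each group will be closely-matched on age, sex, race, and socioeconomic status". It does not say who is skipped, within which strata, or to what tolerance.

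**The concern.** A weighted allele sum depends on allele frequencies. If these differ between ancestries, mean scores can differ for reasons unrelated to alcohol-influenced aggression. Running the discovery GWAS separately by ancestry protects the effect estimates. It does not equalise mean scores in the Spit for Science (S4S) pool, where the ranking is done. If the means differ, the two tails of a single ranking fill with different ancestries.

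Risk group is the exposure in the Aim 4 aggression comparison and in the mediation models. If it tracks ancestry, a difference in noise-blast settings or brain measures cannot be separated from ancestry and its social correlates. Recruitment fixes the composition of the groups, and later adjustment is weak where they barely overlap.

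**Working it through.** **The plan's own figure.** The documents give no figure for ancestry composition by risk group. The imaging sample size reproduces: 198 evaluable + 4 expected to be suspicious of the deception = 202 = 2 x 101.

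**Inputs.** From the documents: race shares 51/19/15/6/9%; 101 per group; an expected S4S sample of 10,000, which is an upper bound on the pool before screening and consent. Assumed: scores are normal with SD 1 within each group, and the mean of the 19% group is shifted by d SD. A shift in the other direction swaps the tails.

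**Mixture calculation, no matching.** For a tail fraction t, find the upper cut-off c from

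0.19 x P(Z > c - d) + 0.81 x P(Z > c) = t.

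The shifted group's share of the high tail is 0.19 x P(Z > c - d) / t. The low tail is treated the same way. Tails of 1.05%, 5% and 10.5% correspond to about 105 people per tail from pools of 10,000, 2,100 and 1,000.

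Worked case, d = 0.5 and t = 0.0105:
- High tail: c = 2.455. The tail probabilities are 0.02527 (shifted) and 0.00704 (unshifted). Check: 0.19 x 0.02527 + 0.81 x 0.00704 = 0.0105. Share = 0.19 x 0.02527 / 0.0105 = 45.7%.
- Low tail: c = -2.249. The shifted group's tail probability is 0.00299. Share = 0.19 x 0.00299 / 0.0105 = 5.4%.

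Share of the 19% group across the three tail sizes:

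| Assumed shift | High group | Low group |
|---|---|---|
| 0 SD | 19% | 19% |
| 0.1 SD | 22-23% | 15-16% |
| 0.25 SD | 26-31% | 11-13% |
| 0.5 SD | 35-46% | 5-8% |
| 1 SD | 53-76% | 1-3% |

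**What this means for matching.** A simulation with all five race shares (300 runs per setting) took the 101 lowest and 101 highest scorers. From the average race shares, the number of race-matched pairs among them is:

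| Assumed shift | Pool 10,000 | Pool 1,000 |
|---|---|---|
| 0 SD | 101 | 100 |
| 0.25 SD | 81 | 87 |
| 0.5 SD | 60 | 74 |
| 1 SD | 26 | 50 |

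At 0.25 SD and a pool of 10,000, about 101 - 81 = 20 people in each group would have to give way to someone nearer the median. The plan has no rule for choosing them.

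**What stratified tails would cost.** The same simulation took tails within race strata in proportion to the shares. Race composition is then identical in both groups by construction. The high-minus-low difference in mean score was:

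| Pool | Within race strata | Single ranking, shifts 0 to 1 SD |
|---|---|---|
| 10,000 | 5.3 SD | 5.3-5.7 SD |
| 2,000 | 4.1 SD | 4.1-4.4 SD |
| 1,000 | 3.5 SD | 3.5-3.8 SD |

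The extra gap under a single ranking arises only as the assumed shift grows. It is the between-group difference that one would want to remove.

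**The case against.** The strongest reply is that the plan foresees this confounding and commits to close matching on race. If that is done, the unmatched splits above do not occur between race categories. Contacted people are also screened before being scheduled, and equal numbers of men and women are required, so passing over candidates is already part of recruitment. All of this stands. The table therefore shows what happens if the contact order is followed without matching, and should be read that way.

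Three stronger readings are tempting, but the documents do not support them.

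- **A reader might infer that the two rules cannot both be followed.** They can. The text sets a contact order and does not require the 101 most extreme scorers to be enrolled. Working inwards within strata meets both rules.
- **A reader might infer that ancestry is certainly loaded onto risk group.** It is not certain. The documents give no score means by ancestry, and at zero shift the tails are 19% and 19%. Ranking across ancestries without adjustment is the natural reading of a single distribution, but it is not stated outright.
- **A reader might infer that the imaging models omit ancestry covariates.** This cannot be asserted. The Phase II Analytic Plan text is broken in the available copy, between the start of the group model and the multiple-comparison paragraph.

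What the reply does not answer is how matching operates during recruitment, and what happens within categories. The matching text says only race, without saying whether this is reported or genetically assigned. The 9% other/multiracial/unknown category in particular can hold wide ancestry differences that matching on the category leaves in place. This residual part has not been quantified.

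**Conclusion.** The point holds conditionally, as a cheap improvement. The plan does not say whether scores are made comparable across ancestries before ranking, or how race matching is combined with the ends-inward order. If the order is applied literally and mean scores differ, risk group is confounded with ancestry. The imbalance is already visible at an assumed 0.25 SD and is absent at zero shift. The sizes rest on normal scores, one shifted group of 19%, and no matching. The promised matching would remove the imbalance between race categories, but not ancestry differences within them.

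**What to change.** In Recruitment and Screening, state that the discovery-derived score will be residualised on ancestry principal components in S4S, or standardised within the ancestry groups defined for the discovery GWAS, before anyone is ranked. This uses genotypes only, so the plan's rule against using the S4S GWAS to build the recruitment score is respected.

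Then fill the low and high groups from the two tails within ancestry-by-sex strata, with the same number from each stratum in both groups. The promised race and sex matching is then built into the contact list, and the equal numbers of men and women can be met by the same quotas. State the tolerance for matching on age and socioeconomic status. Apply the same steps to the fallback score. Include ancestry components as covariates in the group and mediation models if they are not already there.

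The cost is wording and a reordered contact list. S4S is to go through the same GWAS and risk score procedures as the discovery data, so ancestry assignments should be available. The downside is slightly less extreme raw scores in small strata. For example, the 6% stratum needs about 101 x 0.06 / 2 = 3 men per group. If 40% of that stratum are men, they come from about 10,000 x 0.06 x 0.40 = 240 candidates, or 24 in a usable pool of 1,000. The simulation stratified by race only, so the small loss from adding sex is not included in its figures.
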